**1. PROJECT TITLE**

Multicenter Double Blind, Placebo Controlled RCT of modified Qing Fei Pai Du Tang (mQFPD) and Fomitopsis officinalis/Trametes versicolor for COVID-19

Working title:

Mushrooms and Chinese Herbs for COVID-19 (MACH-19)

**4. ESTIMATED DURATION OF THE STUDY**

It is anticipated that 12 months will be required for completion of study activities.

**5. LAY LANGUAGE SUMMARY OR SYNOPSIS (no more than one paragraph)**

Despite biomedical advances, medical intervention for COVID-19 is largely limited to vaccination and supportive care during the later stages of disease. Integrative Medicine offers several promising antiviral and immunomodulatory therapeutics that are available today and warrant studying.

We propose to conduct two multi-center, randomized, double blind, placebo-controlled clinical Phase 1 trials (sub-studies 1a and 1b) to evaluate the safety of: (1) FoTv (a combination of two polypore mushrooms, Fomitopsis officinalis and Trametes versicolor, and (2) mQFPD as a modified form of Qing Fei Pai Du Tang, a Chinese herbal formula that has widely been used in China, Taiwan, and Korea to treat COVID-19 for COVID-19-positive outpatients with mild-to-moderate symptoms assigned to self-quarantined and home management.

Once safety and feasibility have been established in each of these first two sub-studies, we will move forward with a larger Phase 2 study comparing the efficacy of FoTv vs. mQFPD vs. Placebo.

We also herein propose a third, new sub-study, 1c, that will examine the effect of FoTv vs. placebo for use as an adjunct to vaccination for COVID-19 in a general population at the time of COVID-19 vaccination.

Fo and Tv have immunomodulatory properties which may increase antibody titers in response to vaccination more than vaccination alone. However, because they are also immunomodulatory – not purely immune stimulating - they may have the added benefit of simultaneously decreasing vaccine-related side effects following COVID-19 vaccination.

**6. SPECIFIC AIMs**

Sub-study 1a: FoTv vs. placebo in acute COVID-19 patients.

The primary objectives of this study are:

- Ascertainment of safety of FoTv and
- Assessment of feasibility of the intervention (with the primary outcomes focusing on determination of the rates of recruitment and completion)

#### A. Safety:

The following safety data will be collected and assessed during the study:

- 1) Incidence and severity of adverse events
- 2) Laboratory evaluations
- 3) Home glucometer measurements for diabetic participants
- 4) Home blood pressure measurements for hypertensive participants
- 5) Home daily weight measurements for patients with congestive heart failure or diuretic use

Safety data will be collected and assessed using the following methods:

- 1) Each participant will receive a paper copy and an emailed daily diary requesting information on symptoms (including duration and severity), vitals, and medication compliance. Participants who are unable to respond to emails will be asked to directly record this data into the provided paper study daily diary and then will be contacted daily to report this information to the study coordinator. All email exchanges among study personnel will be conducted within the UC intranet secure system. All communications with patients will be through virtual appointments using UC secure systems, UC San Diego encrypted emails or with password-protected study documents.
- 2) Study coordinators will collect and enter all safety data. All serious adverse events (SAEs) will, per UCSD IRB guidelines, be reported to the IRB and DSMB within 3 business days of learning of the event. Any adverse events, as well as any escalation of care, including urgent care, emergency room, or hospitalization, will be reported to the study team after appropriate medical care has been received, via a dedicated phone number or email address that is specific for urgent matters.
- 3) The UCSD site will implement a Data and Safety Monitoring Board (DSMB) to review data safety and monitoring as part of their responsibilities. The DSMB will include two senior researchers and a consumer representative. They will have conference calls bi-weekly (or more frequently, if needed).
- 4) The study biostatistician will send a tabulated symptom and adverse event report daily to all sites and to the study PI and weekly to the study DSMB and IRB.
- 5) The safety of the study medication will also be assessed through laboratory data collection at baseline, and at either the end of the treatments following end of quarantine (for non-hospitalized patients) or as part of hospital admission labs (for patients requiring hospitalization)
  - a. Basic Metabolic Panel
  - b. Complete Blood Count with Differential
  - c. Liver Function Testing
  - d. Prothrombin Time and Partial Thromboplastin Time

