## **9. RESEARCH DESIGN AND METHODS**

The following research design applies to each of the following studies:

Sub-study 1a: FoTv vs. placebo for acute COVID-19 patients

Sub-study 1b: QFPD vs. placebo for acute COVID-19 patients

Sub-study 1c: FoTv vs. placebo as an adjunct to COVID-19 vaccination

Sub-studies 1a and 1b of Phase 1 trial will each be 2-arm multicenter double blind randomized placebo controlled clinical trials.

Each of these safety/feasibility sub-studies will be conducted identically with the exception of additional exclusion criteria that will be required for sub-study 1b on account of the presence of herbal components including ephedrine that require these precautions for avoiding herb-drug interactions.

Sub-study 1c will be a single site double blind randomized placebo controlled clinical trial.

This will be a shorter intervention with broader inclusion criteria.

The research design and methods for the larger efficacy trial (Phase 2) will require analysis of these first two feasibility studies, and the final protocol will be submitted as a future amendment.

The primary objective of sub-studies 1a and 1b will be to assess the safety of FoTv or mQFPD, respectively, when used as therapies for acute COVID-19 infection and feasibility of the study protocol.

The primary objectives of sub-study 1c will be to ascertain the safety of FoTv when used as an adjunct to standard COVID vaccination as well as to evaluate its effects on post-vaccine COVID-19 antibody titers and on vaccination-related side effects.

A total of 66 subjects (33 FoTv or mQFPD and 33 placebo) will be enrolled in each of the 1a and 1b sub-studies.

A total of 266 subjects (133 FoTv and 133 placebo) will be enrolled in sub-study 1c.

The study protocol will be implemented and safety, feasibility, clinical, and laboratory data will be collected.

Interested participants will be asked to contact the study team, who will then conduct screening, consenting, and study enrollment. The study will be open to patients who are

- a) Mildly-to-moderately symptomatic and have tested positive for COVID-19 (sub-studies 1a and 1b)
- b) Scheduled for COVID-19 vaccination (sub-study 1c).

See section 11 for recruitment plan.

Once their eligibility has been confirmed, participants will be randomized to one of two groups by the study statistician:

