### 6. Adverse Events

- Adverse events are being monitored in three formats: daily communication with study team to report symptoms and adverse event reporting as described elsewhere (see section 15), labs at the end of the 14-day treatment period, and urgent reporting of adverse events via a 24 hour physician staffed phone line (see below). The study team will have a daily communication with subjects where our study coordinators will review all subjects' symptoms and their severity. This information will be tallied daily and will be reported to each site's PI and study main PI and medical monitor. Furthermore, they will be reported to the study DSMB and IRB.
- Information regarding occurrence of adverse events will be captured on the IRB approved standard case report form (CRF) as follows: Duration (start and stop dates and times), severity/grade, outcome, and relation to study medication).

- Any deterioration in cardiac or pulmonary status will be immediately escalated to proper medical attention and that any study participant who is hospitalized for any reason will be required to stop study medication irrespective of the cause of this adverse event. These events will subsequently be reported to the DSMB and IRB for review.
- A list of anticipated side effects of FoTv or mQFPD will be available to study coordinators, as will a list of known symptoms of COVID-19. Any reported symptom on the COVID-19 list will be referred to the study participant's primary care provider.

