### **Statistical Methods And Considerations**

For all sub-studies (1a, 1b, and 1c), data management and statistical analysis will be performed by the Krupp Biostatistical and Data Management Core and will employ the Krupp Data System (KDS). A computer-generated randomization list will be prepared by the study biostatistician and will be used to randomize subjects into one of the two treatment groups with equal probability. For sub-study 1c only, equal number of subjects based on age (18-55 and  $>55$ ) and BMI ( $<30$  and  $\geq 30$ ) will be randomized to the treatment groups. For all sub-studies, randomization tables will be prepared at the beginning of the study and will be maintained by the study biostatistician.

Within each of the sub-studies, the comparability of the two treatment groups in terms of baseline demographic and clinical features will be tested with analyses of variance (ANOVAs) for continuous variables and Chi-square analyses for dichotomous variables. Descriptive statistics and exploratory graphing will be used to assess the distribution, normality, and homogeneity of the data. If needed and applicable, the continuous outcome data will be transformed using an appropriate transformation such as a log transformation. Missing data will be examined to assess randomness and informativeness using methods developed by Diggle (1989). Similarly, we will test whether dropout is random or systematic by comparing the dropouts with the study completers in terms of the baseline data. An absence of significant differences would support the random nature of dropout.

The primary aims of our data analytic strategy will be directed toward assessing the safety of the interventions, antibody titers, vaccine side effects, adherence to treatment, and retention rate. This will help to provide guidance to inform any

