required methodological modifications. The safety data will be summarized by treatment group and site. Adverse events will be tabulated. These will include the number of participants for whom the event occurred, the rate of occurrence, and the severity and relationship of adverse events to study treatment. Safety data will be analyzed using ANOVAs for continuous variables and Chi-square analyses for dichotomous variables at each time point. Wilcoxon-Mann-Whitney rank-sum test will be used to analyze treatment arm versus control arm across study visits and sites. We anticipate using non-parametric tests because the majority of the outcome measures used in our research may not be normally distributed. The Kruskal-Wallis test will be used to determine whether samples from each of the two arms originated from the same distribution. Since nonparametric tests are based on complete data and ignore missing follow-up data, general linear mixed regression modeling (Gibbons et al, 1988; Hedeker et al, 199; Laird et al, 1982) will be used to confirm the results of the nonparametric tests. The two arms will be compared over time with a focus on the treatment by Time interaction effect. Mixed regression modeling offers robust handling of missing data (Little, 1996) with an assumption that the data is missing at random. This method allows the inclusion of subjects with missing data or those who were terminated early in the study, without relying on data imputation procedures. This method provides an estimate of the individual variability around the population trend, the variability of the individual intercepts (baseline values) and slopes (changes across time), and the correlation between them. Co-variance structure will be chosen based on Akaike's Information Criterion (AIC). Random group level treatment effects will also be evaluated for importance based on the model AIC. Denominator degrees of freedom will be calculated using the Kenward-Roger small sample correction.

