#### Virulogic risk

According to the WHO, approximately 81% cases of COVID-19 are mild to moderate, and severe disease may require hospitalization in approximately 19% of cases. A total of approximately 5-10% of COVID-19 patients may ultimately require ICU level of care which may include intubation. The CDC estimates the case fatality rate among COVID-19 patients is expected to be between 0.25-3%, with a dramatic increase in death rate among older populations (10 to 27% among persons aged >84 years old). These statistics may change as we learn more about the disease.

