#### Loss of confidentiality

### **15. RISK MANAGEMENT PROCEDURES AND ADEQUACY OF RESOURCES**

Subjects will be monitored throughout the study and their symptoms will be recorded and reviewed by the medical monitor on a daily basis during the active phase of treatment.

Safety of the study medication will also be assessed through laboratory data collection either at the end of the treatments (for non-hospitalized patients) or on hospital admission (utilizing labs on admission for hospitalized patients)

Study participants will be advised to report any skin eruptions to the study team and to stop medication immediately until they can be interviewed by our medical monitor who will make the assessment of allergy.

Respiratory allergies such as asthma exacerbations will be treated as COVID-19 exacerbations, where medication will be stopped and participants will be directed to immediate medical attention. An adverse event will be logged, and relation to the study medication will be determined per protocol.

In an event of participants requiring immediate medical attention, the study team will first refer the patient to contact their primary care physician if they are in close communication. If they are not, the study team will provide the participant with a short list of telephone numbers that patients can call to seek immediate medical attention. This will be specific to Southern California and will include 24-hour hotlines that are run by insurance companies, healthcare centers, and regional governments. If none are appropriate, they will be directed to dial 911.

All serious adverse events (SAEs) will, per UCSD IRB guidelines, be reported to the IRB and DSMB within 3 business days of learning of the event. The study biostatistician will send a tabulated symptom and adverse event report daily to all sites and to the study PI and weekly to the study DSMB and IRB.

Any adverse events, as well as any escalation of care, including urgent care, emergency room, or hospitalization, will be reported to the study team after appropriate medical care has been received, via a dedicated phone number or email address that is specific for urgent matters.

The UCSD site will implement a Data and Safety Monitoring Board (DSMB) to review data safety and monitoring as part of their responsibilities. The DSMB will include two senior researchers, and a consumer representative. They will have a conference call bi-weekly (or more frequently, if needed).

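### The plan describes one safety report for the sites, the PI, the DSMB and the IRB, and gives the DSMB no by-arm report that is withheld from the sites and PI

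*Combined protocol and SAP*

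**What the plan says.** **The report.** Section 6 (Sub-study 1a, A. Safety, method 4) has the study biostatistician "send a tabulated symptom and adverse event report daily to all sites and to the study PI and weekly to the study DSMB and IRB". The sub-study 1b safety section repeats the sentence, and so does Section 15: "The study biostatistician will send a tabulated symptom and adverse event report daily to all sites", with the same further recipients. No version says whether the table is pooled, by coded arm or by named arm.

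**A similar shared flow.** Section 9, Clinical Assessments, item 6 (Adverse Events) has coordinators review symptoms and severity each day. The results are tallied for each site's PI, the "study main PI and medical monitor. Furthermore, they will be reported to the study DSMB and IRB". This item does not mention the biostatistician or treatment arm.

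**Blinding and the allocation list.** Section 9 states that "Sub-studies 1a and 1b of Phase 1 trial will each be 2-arm multicenter double blind randomized placebo controlled clinical trials" and that "Sub-study 1c will be a single site double blind randomized placebo controlled clinical trial". Under Statistical Methods And Considerations, "randomization tables will be prepared at the beginning of the study and will be maintained by the study biostatistician". The same section says that "The safety data will be summarized by treatment group and site", without giving the timing or the recipients of that summary.

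**What else reaches the DSMB.** Serious adverse events are reported within 3 business days (Sections 6 and 15). Hospitalizations and cardiac or pulmonary deterioration are also reported (Section 9, Adverse Events). None of these routes mentions treatment arm. The board holds bi-weekly calls, or more frequent ones if needed. The documents describe no charter, closed session or closed report.

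**The concern.** Staff who run a blinded trial and the board that protects its participants need different tables. Sites and the PI should not see accumulating results by arm. The DSMB needs them, because a comparison with the concurrent placebo group is how a treatment effect is told apart from the disease.

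The need is concrete here. Section 14, on upregulation of IL-1-β and IL-6, records the FDA's concern that FoTv may accelerate or worsen COVID-19. The protocol replies that effects in COVID-19 patients are unstudied and that it relies on the Phase 1 safety study to monitor for them. Such harm would look like the illness under treatment. If the board sees only arms combined, an excess on FoTv and an unlucky run of ordinary disease can give the same table. Safety is also a primary objective of sub-studies 1a and 1b, so this is not a side issue.

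**Working it through.** The plan has no figure of its own to reproduce on this point. The check is a reading of the report flow, followed by a short illustration.

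**Step 1. Who gets what, as written**

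| Recipient | Tabulated report | Other stated input | By-arm content stated? |
|---|---|---|---|
| Sites, PI | daily | daily symptom tally to site PIs and main PI | no |
| Medical monitor | not named as a recipient | daily symptom tally | no |
| DSMB | weekly | same tally information; individual SAE, hospitalization and deterioration reports | no |
| IRB | weekly | same tally information; individual SAE, hospitalization and deterioration reports | no |

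No row gives the DSMB a by-arm view that the sites and PI do not have.

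**Step 2. Which form does the report take?** The trials are declared double blind, and the sentences about the report do not mention treatment group. Pooled is the natural reading. The biostatistician holds the randomization tables, so a by-arm table would be possible, but nothing says that one is sent.

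**Step 3. What a pooled table can show.** Inputs:
- 33 participants per arm and 66 in total in each of sub-studies 1a and 1b (Section 9).
- Event counts are assumed; the documents give none for this population.

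For a total of t events, the pooled rate is t/66, which depends only on t. For the comparison between arms, the probability of a events in one arm given t is C(33, a) × C(33, t − a) / C(66, t). The two-sided Fisher p-value adds the probabilities of all splits no more likely than the one observed.

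Take t = 10 and a split of 1 v 9:
- C(66, 10) = 210,980,549,208.
- The 1 v 9 split: C(33, 9) × C(33, 1) = 1,272,714,300.
- The 0 v 10 split: C(33, 10) × C(33, 0) = 92,561,040.
- Two-sided p = 2 × (1,272,714,300 + 92,561,040) / 210,980,549,208 = 0.0129.

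| Total events | Pooled rate | Split | Rates by arm | Fisher p |
|---|---|---|---|---|
| 10 | 15.2% | 5 v 5 | 15.2% v 15.2% | 1.00 |
| 10 | 15.2% | 1 v 9 | 3.0% v 27.3% | 0.013 |
| 14 | 21.2% | 7 v 7 | 21.2% v 21.2% | 1.00 |
| 14 | 21.2% | 3 v 11 | 9.1% v 33.3% | 0.033 |
| 14 | 21.2% | 2 v 12 | 6.1% v 36.4% | 0.005 |

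Within each total, the pooled line is the same whatever the split. The p-values only describe how far apart the arms are; they are not proposed as a monitoring boundary.

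**The case against.** **The gap is one of silence.** The documents do not state the form of the report, and nothing stops the DSMB from asking the biostatistician for by-arm data on one of its calls. A charter outside these documents may provide for it. This stands. A reader might infer that the DSMB will never see the arms apart, but the text supports only that no such report is specified.

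**The sites may look unblinded.** A reader might join the by-group and by-site summary to the daily report and conclude that the sites receive results by arm, or that small cells reveal individual allocations. The documents do not support this. That summary sits among the analysis methods and never mentions the daily report. The daily tally under Adverse Events is built from coordinators' symptom reviews, and nothing says that it is split by arm.

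**Pooled data are not useless.** A pooled rate well above expectation would raise an alarm, and serious events also reach the board one by one. This is true, but an alarm does not say which arm is affected, and the protocol gives no expected rate for the population it enrols.

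**The 19% figure.** Section 14 says that "severe disease may require hospitalization in approximately 19% of cases". It is tempting to note that, say, 13 of 66 (19.7%) would then look ordinary even if most events were on one arm. That comparison fails. The 19% covers all COVID-19 cases, whereas sub-studies 1a and 1b enrol mildly to moderately symptomatic outpatients and exclude people with symptoms that call for hospitalization. If their true rate were 5% or 10% (assumed), 13 or more of 66 would have binomial probability 0.00002 or 0.013, and a pooled table would stand out. The illustration above does not use the 19%.

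**Conclusion.** The concern holds in limited form. As written, the plan specifies one tabulated report for operational staff and for the board, and no by-arm report reserved for the DSMB. On the natural pooled reading, the board's stated inputs cannot separate a treatment-driven worsening from the disease itself. The same 15.2% pooled rate fits arms that are equal and arms at 3.0% v 27.3%.

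This rests on the documents supplied being the full description of monitoring, and on assumed event counts that illustrate the masking and do not predict it. The specific FDA concern is about FoTv in COVID-19 patients, so it bears most directly on sub-study 1a. The report wording is the same for 1b, and Section 15 is not limited to one sub-study. The point should be fixed, but it is not evidence that the blind is broken.

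**What to change.** In Section 6 (A. Safety, sub-studies 1a and 1b) and Section 15, and consistently in Section 9 under Adverse Events, replace the single report with two:

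1. **Open report.** For the sites, PI, medical monitor and IRB: pooled across arms, with no arm identifiers, at the frequencies already stated.
2. **Closed report.** For the DSMB alone, for its scheduled calls: by coded arm, with numbers randomized and exposed, participants with each adverse event and serious adverse event, and hospitalizations. Name who prepares it.

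In Statistical Methods And Considerations, add that the by-group safety summary is not released to the sites or the PI before database lock.

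The cost is about a paragraph of protocol text, a second table shell from the same data, and the need to keep the closed report confidential. The biostatistician who already holds the randomization tables could prepare it, so no added staff are required. No dose, visit, sample size or clinical rule changes.
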